5.1. Overall Design

Study I4V-MC-JAIM [JAIM] is a Phase 3, multicenter, randomized, outpatient, long term extension trial to evaluate the long-term safety and efficacy of baricitinib in eligible patients with SLE who have completed the treatment period in an originating study (such as, Study I4V-MC-JAHZ [JAHZ] or Study I4V-MC-JAIA [JAIA]).

Figure JAIM.1 illustrates the study design.

The study consists of 3 periods:

[figure not shown]
Screening Period: Screening for JAIM (Week 0, Visit 1) should occur during the last visit of the originating study. However, in particular circumstances, this duration may be extended after consultation with the sponsor.

Treatment Period: Patients randomized to active treatment, baricitinib 4-mg daily or baricitinib 2-mg daily, during the originating studies will continue on the same, blinded dose of baricitinib in Study JAIM. Patients randomized to placebo during the originating studies will be randomized 1:1 to receive blinded baricitinib 2-mg or 4-mg daily during Study JAIM. Randomization will be stratified by corticosteroid dose on the day of randomization (<10 mg/day; ≥10 mg/day of prednisone or equivalent), and region (defined in the statistical analysis plan [SAP]). Patients originally randomized to active treatment in originating study with renal impairment at baseline of the originating study will not receive doses higher than 2-mg baricitinib QD. Patients randomized to placebo in the originating study with renal impairment (defined as estimated glomerular filtration rate [eGFR] <60 mL/min/1.73 m²) at the time of randomization to JAIM (assessed by the most recent eGFR from the originating study) will receive 2-mg baricitinib QD. The treatment period will last up to 156 weeks from enrollment into Study JAIM.

Patients may continue to receive the background standard therapies for SLE, including a corticosteroid, a single antimalarial, and/or a single immunosuppressant, that they were receiving at completion of the originating study.

Throughout the trial, investigators should continue to assess individual benefit-risk for patients to remain in the trial and should consider discontinuing patients if sufficient clinical benefit is not observed with protocol-permitted treatments.

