## 5. Study Design

### 5.1. Summary of Study Design

Study I4V-MC-JAIM (JAIM) is a Phase 3, multicenter, randomized, outpatient, long term extension trial to evaluate the long-term safety and efficacy of baricitinib 4-mg and 2-mg in eligible patients with systemic lupus erythematosus (SLE) who have completed the treatment period in an originating study (such as, Study I4V-MC-JAHZ [JAHZ] or Study I4V-MC-JAIA [JAIA]). Study JAIM will enroll patients who have completed treatment through week 52 of Study JAHZ or Study JAIA and meet eligibility requirements.

Abbreviations: QD = once daily; V = visit.

a Visit 1 of Study JAIM should be completed on the same calendar day as the Week-52 visit of the originating study.

b The follow-up visit should occur 4 weeks ( $\pm 5$  days) after the last dose of study drug.

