## 6. A Priori Statistical Methods

### 6.1. General Considerations

This Statistical Analysis Plan (SAP) describes analyses that will be utilized for the full clinical study report (CSR) for Study JAIM, at the time of JAIM primary outcome database lock. Analyses to be produced prior to the JAIM primary outcome database lock, for purposes of regulatory submissions, will be identified in the retained list of analyses. Additional safety analyses that integrate data from the originating studies will be specified in the integrated safety analysis plan (ISAP) for SLE. Any exploratory analyses will be described in a separate document. Statistical analysis of this study will be the responsibility of Eli Lilly and Company or its designee.

Not all displays described in this SAP will necessarily be included in the CSR. Not all displays will necessarily be created as a “static” display. Some may be incorporated into interactive display tools such as Spotfire instead of, or in addition to, a static display. Any display described in this SAP and not included in the CSR would be available upon request.

Throughout this document, references to analyses of corticosteroids refer to analyses of systemic corticosteroids, unless otherwise specified.

Statistical analyses of categorical safety and efficacy endpoints will be descriptive in nature.

Frequency counts and percentages by treatment arm (see [Table JAIM.6.1](#)) will be provided for the safety and efficacy endpoints. For non-model-based efficacy endpoints, 95% confidence intervals (CIs) for single proportions using the Wilson Score (Wilson, 1927; Newcombe, 1998) method will be utilized.

Unless otherwise stated, inferential statistical analyses (p-values and 95% CIs) which compare treatment groups will not be conducted.

For continuous efficacy and health outcomes endpoints the significance of within-treatment group changes from baseline will be evaluated by testing whether the treatment group least squares mean (LS mean) changes from baseline are different from zero; the 95% CI and the standard error for the LS mean change will also be displayed.

Change from baseline (defined in [Section 6.3](#)) will be calculated as the postbaseline (at that visit) value minus the baseline value. If all baseline values are missing for a particular variable, the change from baseline and percent change from baseline will not be calculated.

[Table JAIM.6.1](#) summarizes the treatment arms based on the treatment assigned in JAIM.

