### 6.3. Definition of Baseline and Postbaseline Periods

For efficacy analyses, *baseline* for patients receiving active treatment (baricitinib 2-mg and 4-mg) in originating studies (JAHZ and JAIA) is defined as the last nonmissing measurement taken in the originating studies, prior to starting study medication. *Baseline* for patients receiving placebo in originating studies is defined as the last nonmissing assessment prior to the first dose of active study drug given in Study JAIM Visit 1 (Week 0). Any assessment collected after the JAIM Visit 1 dose through the date of Visit 11 or the early discontinuation visit is defined as *postbaseline* for the Treatment Period.

Protocol-defined visit windows are defined as  $\pm 4$  days for Visit 2 (Week 4),  $\pm 7$  days for Visit 3 (Week 12),  $\pm 10$  days from Visit 4 (Week 24) until Visit 7 (Week 60), and  $\pm 14$  days from Visit 8 (Week 84) until Visit 11 (Week 156). If there are data within the protocol-defined window, those data will be used in by-visit analyses. If a protocol-defined visit is missing, then the nearest unscheduled visit data that exist will be mapped to that visit and included in by-visit analyses.

For safety analyses, baseline is defined as the last nonmissing scheduled (planned) measurement prior to the first dose of baricitinib administration in Study JAIM for continuous measures by-

visit analyses and all nonmissing measurements prior to the first dose of the study drug administration (baricitinib) in Study JAIM for all other analyses.

Postbaseline measures for the safety analyses are defined as the nonmissing scheduled (planned) measurements after the first dose of baricitinib administration in Study JAIM for continuous measures by-visit analyses and all nonmissing measurements after the first dose of the study drug administration (baricitinib) in Study JAIM for all other analyses.

In general, when the baseline measurement is collected on the same day (where time is not collected) as the first dose date, this measurement will be used as the baseline value for efficacy and safety except adverse events (AEs).

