## 6.4. Analysis Methods

Continuous efficacy and health outcome variables, except for Systemic Lupus International Collaborating Clinics (SLICC)/American College of Rheumatology (ACR) Damage Index will use a restricted maximum likelihood-based mixed model for repeated measures (MMRM) analysis. The response variable will be change from baseline across postbaseline visits. The model will include the following explanatory variables as fixed factors: treatment, baseline disease activity (total SLEDAI-2K  $<10$ ;  $\geq 10$ ), baseline corticosteroid dose ( $<10$  mg/day;  $\geq 10$  mg/day prednisone or equivalent), region (North America, Central/South America/Mexico, Europe, Asia and Rest of World), visit (as categorical variable), baseline value, treatment-by-visit interaction, and baseline value-by-visit interaction. Within-patient variance-covariance errors will be modeled using an unstructured covariance matrix. If this analysis fails to converge, the following structures will be tested in this pre-specified order: 1) heterogeneous Toeplitz (TOEPH), 2) heterogeneous autoregressive (ARH[1]), 3) heterogeneous compound symmetry (CSH), and 4) autoregressive (AR[1]). The Kenward-Roger method will be used to estimate the degrees of freedom. For each treatment group the least squares mean (LS mean), standard error, within-treatment p-value, and 95% CIs will be reported.

Systemic Lupus International Collaborating Clinics (SLICC)/ACR Damage Index change from baseline will be summarized with observed and modified last observation carried forward (mLOCF).

The binary efficacy measures will be summarized with observed case and non-responder imputation (NRI).

For both efficacy and safety evaluations, if study drug is temporarily interrupted (suspended) during a treatment period, the measurements taken during the temporary interruption will be included in the analysis.

Both observed and imputed analyses will be performed for efficacy and health outcomes measures.

All analyses will include the treatment arms given in [Table JAIM.6.1](#).

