### **6.4.1. Adjustments for Covariates**

Randomization in the originating studies is stratified according to disease activity (total SLEDAI-2K at screening  $<10$ ;  $\geq 10$ ), corticosteroid dose at baseline ( $<10$  mg/day;  $\geq 10$  mg/day prednisone or equivalent), and region (North America, Central/South America/Mexico, Europe, Asia and Rest of World). Therefore, these factors will be adjusted for as described in Section 6.4.

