### 6.4.2.3. Mixed Model for Repeated Measures

For continuous variables, an MMRM analysis with a missing at random assumption for handling missing data will be performed. This likelihood-based analysis takes into account both missingness of data and the correlation of the repeated measurements.

The MMRM method may be justified when the estimand of interest uses the hypothetical strategy (EMA2020) for handling intercurrent events. In this strategy, the scientific question of interest is to assess the effect of study treatment in a hypothetical trial where all patients have complete data and continue to take study treatment as directed without dropping out of the study.

For patients who have prohibited medication use any time after baseline, any observed data after the date of the prohibited medication use will be excluded from the MMRM analysis. The earliest date of prohibited medications will be used for censoring.

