Systemic Lupus International Collaborating Clinics/American College of Rheumatology Damage Index (SLICC/ACR)	SLICC/ACR Damage Index assesses damage to 12 organ systems regardless of its cause.	SLICC/ACR Damage Index Score	Calculated as the sum of all available entries with a maximum score of 47.	“Missing” item is coded as 0.
Worst Pain NRS	This Worst Pain NRS is a single-item patient-administered 11-point horizontal scale anchored at 0 (no pain) and 10 (pain as bad as you can imagine)	Worst Pain NRS score	Permitted range of values is from 0 to 10.	Single item, missing if missing.
FACIT-Fatigue	The FACIT-Fatigue scale (Cella and Webster 1997) is a 13-item symptom-specific questionnaire that assesses self-reported severity of fatigue and its impact upon daily activities and functioning.	FACIT-Fatigue total score	The FACIT-F uses 0 (“not at all”) to 4 (“very much”) numeric rating scales to assess fatigue and its impact in the past 7 days. Scores range from 0 to 52 with higher scores indicating less fatigue. The FACIT-Fatigue Scoring Guidelines (Version 4) will be used to calculate the Total Score. Reversals are needed for all items except An5 and An7, as described in scoring manual. http://www.ser.es/wp-content/uploads/2015/03/FACIT-F_INDICE.pdf .	Missing items are acceptable as long as more than 50% of the items are answered (ie, a minimum of 7 out of 13 items), the sum of available items will be multiplied by 13 then divided by the number of items answered to obtain the total score. If less than 7 items are answered, the FACIT-Fatigue total score will be set to missing.
Steroid sparing	This measures the change in corticosteroid dose through week 156	Corticosteroid Dose	See Section 6.10.1 for detailed derivations.	No minimum data requirement.
Worst Joint Pain NRS	This Worst Joint Pain NRS is a single-item, patient-administered 11-point horizontal scale anchored at 0	Worst Joint Pain NRS Score	Permitted range of values is from 0 to 10.	Single item, missing if missing.

Measure	Description	Variable	Derivation/Comment	Definition of Missing
	(no joint pain) and 10 (joint pain as bad as you can imagine)			
Worst Fatigue NRS	This Worst Fatigue NRS is a patient-administered 11-point horizontal scale anchored at 0 (no fatigue) and 10 (fatigue as bad as you can imagine)	Worst Fatigue NRS Score	Permitted range of values is from 0 to 10.	Single item, missing if missing.

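### One MMRM pools arms whose baselines are about 52 weeks apart, so LS means taken at the all-arm baseline can misstate each arm's change and, in the placebo-to-baricitinib arms, alter the test against zero

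*SAP*

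**What the plan says.** SAP 6.3 uses two efficacy baselines. Arms on baricitinib in JAHZ or JAIA use the last value before study drug in that trial. Baseline "for patients receiving placebo in originating studies is defined as the last nonmissing assessment prior to the first dose of active study drug", that is, JAIM Week 0. SAP 5.1 fixes the distance between the two: "Visit 1 of Study JAIM should be completed on the same calendar day as the Week-52 visit of the originating study".

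SAP 6.4 models change from baseline in one MMRM covering the four efficacy arms of Table JAIM.6.1. Its terms include "baseline value, treatment-by-visit interaction, and baseline value-by-visit interaction". There is no treatment-by-baseline term, so all arms share one slope at each visit. SAP 6.4.1 adds the originating-study stratification factors: "Therefore, these factors will be adjusted for as described in Section 6.4".

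For each arm the SAP reports an LS mean, standard error, 95% CI and within-arm p-value. SAP 6.1 evaluates within-arm change by "testing whether the treatment group least squares mean (LS mean) changes from baseline are different from zero". No between-arm test is planned. Neither document states the baseline value, or the weights for the category factors, at which the LS means are evaluated.

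**The concern.** In a randomised trial with one baseline visit, arm mean baselines differ only by chance, and the reference baseline for an LS mean hardly matters. Here the definition itself creates two kinds of baseline: values before treatment, and values after about a year on placebo plus background therapy. Their means may well differ.

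If they do, and the slope is not zero, LS means at the all-arm average describe a hypothetical patient whose baseline belongs to neither group. A switching arm's estimate, CI and p-value would partly reflect where other patients stood before treatment in the originating study. With a negative slope, switching arms that start less severe are pushed towards improvement and continuing arms towards no change. If the switching arms start more severe, the directions reverse. On scales such as FACIT-Fatigue ("Scores range from 0 to 52 with higher scores indicating less fatigue"), SF-36 and EQ-5D VAS, less severe means a higher score.

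The practical risk is that a switching arm with no real change is reported as significantly improved.

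**Working it through.** **Inputs from the documents.** About 1100 patients (Protocol 10.1); former placebo patients randomised 1:1 (SAP 5.3); two-sided 5% level (Protocol 10.3.1); baselines about 52 weeks apart. The plan states no SD, slope, arm baseline or effect size for these endpoints, so there is no figure of its own to reproduce.

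**Assumptions.** Originating allocation 1:1:1, giving 367/367/183/183; SD 3.5 at baseline and follow-up; baseline-to-follow-up correlation r of 0.3 to 0.7, so the slope for change is r − 1 = −0.7 to −0.3; switching arms less severe by a gap g; true switching change 0; true continuing change −5.0.

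**Size of the shift.** LS mean at the all-arm baseline = own-arm mean change + slope × (all-arm mean baseline − arm mean baseline).

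- Switching arms: 734/1100 × (0.3 to 0.7) = 0.20 to 0.47 of the gap, towards improvement.
- Continuing arms: 366/1100 × (0.3 to 0.7) = 0.10 to 0.23 of the gap, towards no change.
- If g = 0 or the slope is 0, the shift is zero.

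**Approximate effect on the test, g = 1.** Residual SD = 3.5 × √(1 − r²), and SE ≈ residual SD / √183.

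| r | Residual SD | SE | Shift | Shift/SE | Rejection of zero |
|---|---|---|---|---|---|
| 0.3 | 3.34 | 0.247 | −0.467 | 1.89 | 47% |
| 0.5 | 3.03 | 0.224 | −0.334 | 1.49 | 32% |
| 0.7 | 2.50 | 0.185 | −0.200 | 1.08 | 19% |

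**Simulation.** Four-visit MMRM, unstructured covariance, between-visit correlation 0.7, r = 0.3, 0.5 and 0.7. Entries are rejection rates for one switching arm at the last visit when its true change is 0.

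| Gap | Pooled, complete data (2000 replicates) | Pooled, 60% observed at last visit, missing at random (1000 replicates) |
|---|---|---|
| 0 | 4.5–6.5% | 4.4–6.5% |
| 0.5 | 8.1–17.2% | not run |
| 1 (0.29 SD) | 19.1–45.2% | 12.7–37.5% |
| 2 (0.57 SD) | 56.5–95.7% | 39.2–88.9% |

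With complete data, the switching arm's LS mean was −0.20 to −0.46 at gap 1 and −0.40 to −0.94 at gap 2.

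**Further checks.**

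- Slope 0: rejection is 5.6% and 5.5% at gaps 1 and 2 (single visit).
- Higher-is-better scale, switching arms 0.29 SD less severe: false improvement of 0.057 to 0.134 SD and 19.6–47.5% rejection (single visit).
- Masking: with a true worsening of +1, gap 4, slope −0.5, residual SD 3.5 and 110 patients in the arm, the LS mean is −0.35. Rejection falls from 81% at the own-arm mean to 18%, with the sign reversed.
- Continuing arms: at gap 1, −5.0 + (0.10 to 0.23) gives −4.9 to −4.8. At gap 2, −5.0 + (0.20 to 0.47) gives −4.8 to −4.5. Zero is rejected in every replicate either way.

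**Alternatives.**

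- Separate models: LS mean within 0.02 of zero; rejection 5.1–9.6% with complete data and 4.2–8.3% with dropout. SE ratio to the pooled model is 0.985 to 1.011, in a simulation without region terms.
- Observed own-arm mean change: 3.1–6.1% when dropout is unrelated to earlier change, but 14.8–97.9% when the log-odds of dropout depend on it at 0.5 to 1.0 per SD.
- Category weights in the separate switching model (28% with SLEDAI-2K ≥10, factor effect 0.2 to 0.4 SD, both assumed; 1500 replicates): equal weights shift the LS mean by 0.04 to 0.09 SD (10.9–33.1% rejection). Observed weights give 0.00 SD (5.8–9.7%).

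**The case against.** The strongest reply is that the SAP never says LS means are taken at the all-arm mean. That is a software convention, so the documented gap is an unstated reference value. An LS mean at a common baseline is also a valid estimate for a patient at that baseline. This is right as far as it goes, but SAP 6.1 presents the LS mean as the arm's own change from baseline, and the usual default does not deliver that.

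Second, SAP 6.4 and 6.4.2.1 plan observed-data summaries, and Appendix 2 tabulates baselines by arm, so a reader could see a gap. These would reveal the shift but would not correct the reported MMRM estimate, CI and p-value. Table JAIM.6.4 lists only MMRM for these endpoints. Observed means are also fragile here, because Protocol 5.1 says investigators "should consider discontinuing patients if sufficient clinical benefit is not observed with protocol-permitted treatments", which ties dropout to response.

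Third, the pooled model could be kept with LS means at each arm's own baseline. That removes the shift, but it was somewhat less well calibrated (about 7–11% rejection, against about 5–9% for separate models in the same check). Splitting does carry a burden. Ten postbaseline visits give 10 × 11 / 2 = 55 covariance parameters per model, with about 366 patients in the switching model before dropout. The fallback structures in SAP 6.4 cover non-convergence, although the two models could then end with different structures.

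Two points stand. The size of the effect rests on assumptions, and the main simulation used four visits without the region, SLEDAI-2K and corticosteroid factors. The scope is also limited: secondary endpoints, no between-arm inference, and a primary objective of safety.

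**Conclusion.** The concern holds. The two baseline definitions, the single model with a shared slope, and the test of each arm against zero are all SAP text; the shift then follows algebraically once LS means are evaluated at the all-arm mean. It requires unequal mean baselines and a non-zero slope.

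The documents cannot say how large it will be. One loose pointer is the Phase 2 placebo SRI-4 rate of 47.6% at Week 24 (Protocol 3.1), a response that requires a SLEDAI-2K fall of at least 4 points. If the remaining patients did not worsen on average, the mean fall is at least 0.476 × 4 = 1.9 points. That is another study and an earlier week, but it suggests that gaps of 1 to 2 points are not extreme. Under the assumptions above, gaps of that size raise a switching arm's false rejection rate from about 5% to between 19% and 96% with complete data. For continuing arms with a large true change the effect is a modest understatement that is unlikely to change the test.

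This should be fixed before the MMRM results are reported. It does not affect the primary safety objective.

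**What to change.** In SAP 6.4:

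- Fit the two continuing arms in one MMRM and the two placebo-to-baricitinib arms in another, keeping SAP 6.4.2.3, under which "an MMRM analysis with a missing at random assumption for handling missing data will be performed".
- Evaluate LS means at the mean baseline of each model's own patients, with observed rather than equal weights for the category factors.
- Label the within-arm p-values descriptive, or drop them. Both models treat baseline as fixed, and rejection of about 4–10% under no change remains.
- Do not substitute the observed own-arm mean change for the MMRM inference.

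The cost is SAP wording, a model split and a second covariance matrix to fit, with less pooling of covariate information. Standard errors changed by at most 1.5% in the simulation. No new data are needed.

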
**Table JAIM.6.1. Treatment Arms**

JAIM Treatment Arms	Description for Patients from JAHZ/JAIA
Baricitinib 2-mg	All patients randomized in the originating studies to baricitinib 2-mg QD (They will remain on baricitinib 2-mg during JAIM).
Baricitinib 4-mg	All patients randomized in the originating studies to baricitinib 4-mg QD (They will remain on baricitinib 4-mg during JAIM).
Placebo to baricitinib 2-mg	Patients randomized to Placebo at Week 0 of JAHZ/JAIA and subsequently randomized to baricitinib 2-mg at Week 0 (Visit 1) in JAIM.
Placebo to baricitinib 4-mg	Patients randomized to Placebo at Week 0 of JAHZ/JAIA and subsequently randomized to baricitinib 4-mg at Week 0 (Visit 1) in JAIM.
Additional JAIM Treatment Arms for Safety	
Pooled baricitinib	Patients treated with baricitinib 2-mg or 4-mg QD in Study JAIM.

Abbreviation: QD = once daily.

